7.1 Discontinuation of Study Intervention

It may be necessary for a participant to permanently discontinue (definitive discontinuation) study intervention.

Participants may be discontinued from study intervention in the following situations:

- Participant decision. The participant is at any time free to discontinue treatment, without prejudice to further treatment
- An AE that, in the opinion of the Investigator or AstraZeneca, warrants discontinuation from further dosing
- Severe non-compliance with the CSP
- Safety reasons as judged by the investigator and/or sponsor where continued treatment may put participant at undue risk

Participants will be discontinued from study intervention in the following situations:

- If the participant becomes pregnant during the course of the study
- Protocol-defined hyperkalaemia: Study treatments must be discontinued in case of confirmed (ie, 2 consecutive samples) serum/plasma K⁺ > 6.0 mmol/L, or confirmed serum/plasma K⁺ > 5.5 mmol/L (at investigator's discretion), or serum/plasma K⁺ > 5.5 mmol/L with repeat value > 6 mmol/L (see Appendix F 1 for details on the monitoring and management of hyperkalaemia)
- Protocol-defined deteriorating renal function: Study treatments must be discontinued in case of confirmed eGFR reduction from baseline > 50% and/or any confirmed decrease below 15 mL/min/1.73 m² (see Appendix F 2 for details on the monitoring and management of deteriorating renal function)
- There have been reports of ketoacidosis, including DKA, in patients with T2DM taking dapagliflozin and other SGLT2 inhibitors in previous studies. Patients with T2DM on investigational treatment who present with signs and symptoms consistent with ketoacidosis, including nausea, vomiting, abdominal pain, malaise and shortness of breath should be assessed for ketoacidosis, even if blood glucose levels are < 14 mmol/L (250 mg/dL). If ketoacidosis is suspected, discontinuation or temporary interruption of the investigational treatment should be considered and the patient should be promptly evaluated.

Note that discontinuation from study intervention is NOT the same thing as a withdrawal from

the study.

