contributed to hyperkalaemia; and/or continuation with reassessment; or permanent discontinuation.

- If the repeat local laboratory sample has serum/plasma $K^+ \le 5.5 \text{ mmol/L}$, then study treatments can be resumed, even if the central laboratory sample has serum $K^+ > 6.0 \text{ mmol/L}$.

If the investigator is aware of any change in the participant's clinical status that may influence serum electrolyte levels or fluid balance (eg, vomiting and/or diarrhoea > 1 day), it is recommended to reassess serum/plasma K^+ levels as soon as possible after the acute event. In case of permanent discontinuation, serum/plasma K^+ levels should be monitored until resolution or stabilisation.

F 2 Deterioration of Renal Function

Serum creatinine will be measured both at a local laboratory and a central laboratory at all baseline and on-treatment visits according to the SoA. Repeat samples should be sent for both central and local laboratory assessment. It is expected that local laboratory results will be available prior to central laboratory results. As local and central laboratories will calculate eGFR using different formulas, central eGFR values should always be compared to central eGFR values and local eGFR values should always be compared to local eGFR values. For local laboratories, the eGFR assessment at Visit 3 (prior to the start of study treatment) will be taken as the baseline eGFR value.

- If eGFR shows a 30-50% decline from baseline and an absolute value ≥ 15 mL/min/1.73 m² (based on local and/or central laboratory samples), eGFR should be reassessed within 1 week.
 - If persistent 30-50% decline stabilises upon weekly follow-ups, eGFR monitoring may return to the standard SoA, at investigator's discretion.
- If eGFR shows a >50% decline from baseline and/or decreases to an absolute value < 15 ml/min/1.73 m² (based on local and/or central laboratory samples), eGFR should be reassessed within 48 hours.
 - If eGFR shows a 30% to 50% decline from baseline and an absolute value $\geq 15 \text{ mL/min/1.73 m}^2$, eGFR should be reassessed within 1 week.
 - If eGFR again shows a >50% reduction from baseline and/or absolute value
 <15 mL/min/1.73 m², study treatments must be discontinued immediately and eGFR should be followed up within a week and weekly until signs of improvement and stabilisation.

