#### 4.11.2 Adverse Events

All AEs will be recorded from the time of randomisation and SAEs will be recorded from the time of signing the full ICF for the study (Visit 1a). No AE or SAE information will be collected after just signing of the optional pre-screening ICF. Recording of all AEs will continue until the end of the participant's safety follow-up period.

All AEs will be coded using the most recent version of the MedDRA that will have been released for execution at AstraZeneca or designee.

When not otherwise specified only AEs occurring with an onset date, or worsening, on or after first dose of investigational medical product (IMP) and within 28 days after last dose of IMP will be summarized.

The following rules will be used to determine whether or not an AE has taken place on-treatment:

- 1. An AE with an onset date and time on or after the date and time of first dose up to and including 5 days following the date and time of last dose of study treatment will be considered on-treatment
- 2. An AE with an incomplete start date and whose end date is not prior to the time of dosing on Day 1 will be considered to have taken place on-treatment unless the non-missing components of the incomplete start date indicate that the start date falls outside the time from dosing on Day 1 to last dose plus 5 days

The following variables will be collected for each AE:

- Adverse event diagnosis/description (verbatim)
- The date and time when the AE started and stopped
- Maximum intensity
- Whether the AE is serious or not
- Investigator causality rating against the investigational medicinal product AZD9977 and/or the investigational product Dapagliflozin (yes or no)
- Action taken with regard to investigational products (AZD9977 and/or Dapagliflozin)
- Adverse event caused subject's withdrawal from the study (yes or no)
- Outcome

Unless otherwise specified, all summaries will be provided by treatment group for the SS.

The number and percentage of AEs will be presented by SOC and/or PT and for each eGFR category.

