### Deteriorating renal function related safety topics of interest

- Number (%) of patients with a decrease in eGFR of  $\geq 25\%$ ,  $\geq 30\%$ ,  $\geq 40\%$  and  $\geq 57\%$ from baseline at any visit during the randomized treatment period (based on central lab values). These decreases would need to be confirmed by another central eGFR measure. Summary will be based on the on-treatment definition included in section 4.11.2
- Number (%) of patients who met the protocol mandated renal discontinuation criteria in the study:
  - At any visit during the randomized treatment period eGFR >50% decline from baseline and/or decrease to an absolute value <15 ml/min/1.73 m^2 confirmed with eGFR >50% decline from baseline and/or decrease to an absolute value <15 ml/min/1.73 m^2 (based on central lab values).

Confirmation has to be the next consecutive central lab sample which is  $\leq 14$  days of the original central lab sample.

Additional analysis will include eGFR lab values confirmed at the next consecutive central lab sample regardless of time from initial lab sample.

- Number (%) of patients with >25% residual decrease in eGFR at safety follow-up visit compared to baseline
- Number (%) of patients who discontinued due to meeting the protocol mandated renal discontinuation criteria in the study

†Based on the end of treatment CRF page

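### The confirmed eGFR-decline rows in SAP 4.11.3 close 5 days after last dose, so falls that deepen or are first confirmed after the renal stop rule has acted may be missed

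*Protocol*

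**What the plan says.** Protocol 7.1 requires permanent discontinuation for "confirmed eGFR reduction from baseline > 50% and/or any confirmed decrease below 15 mL/min/1.73 m²". Appendix F 2 gives the mechanics. When a value first crosses either limit, "eGFR should be reassessed within 48 hours", and no pause in dosing is ordered while the repeat is awaited. "Repeat samples should be sent for both central and local laboratory assessment". If the repeat also crosses, "study treatments must be discontinued immediately and eGFR should be followed up within a week and weekly until signs of improvement and stabilisation". The trigger may be a local or a central value, and the two laboratories use different eGFR formulas.

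SAP 4.11.3 tabulates patients with eGFR falls of at least 25, 30, 40 and 57%, using central values. Of confirmation it says: "These decreases would need to be confirmed by another central eGFR measure". Of the window it says: "Summary will be based on the on-treatment definition included in section 4.11.2". That definition was written for adverse events. It runs from first dose "up to and including 5 days following the date and time of last dose".

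The same SAP section also gives a row for patients meeting the renal discontinuation criteria, a row for a residual fall above 25% at the safety follow-up visit, a by-visit summary of central eGFR, and renal preferred terms. All are repeated by baseline eGFR category.

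**The concern.** The outcome being counted helps to close its own counting window. Once a fall is deep enough to stop drug, the clock runs out 5 days later. Yet Appendix F 2 requires a sample within a week and weekly samples after that. The first of these may fall inside or outside the 5 days; the later ones fall outside. They are unscheduled, so the SAP specifies no summary table for them.

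Deteriorating renal function is one of three named safety topics. If an active dose triggers more stops than dapagliflozin alone, more of its later eGFR values leave the threshold rows. Where those values show further decline, the comparison of severe falls would be pulled toward no difference.

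**Working it through.** **Inputs.** Stop limits: a fall above 50%, or eGFR below 15 (Protocol 7.1, Appendix F 2). Row thresholds t: 25, 30, 40 and 57% (SAP 4.11.3). Window: last dose plus 5 days (SAP 4.11.2). The plan states no rate or power for these rows, so there is no figure of its own to reproduce.

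**Step 1: where the stop falls.** For baseline b, measured centrally, the stop limit is a fall of min(50%, 1 − 15/b).

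| Baseline b | Fall at which the stop applies |
|---|---|
| 20 | above 25.0% |
| 22 | above 31.8% |
| 25 | above 40.0% |
| 27 | above 44.4% |
| 30 or more | above 50% |

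**Step 2: which rows lie beyond it.** A row at t lies beyond the stop limit if t exceeds 50%, or if b is below 15/(1 − t).

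- 25%: 15/0.75 = 20.0, so the row is unaffected at baselines of 20 or more.
- 30%: 15/0.70 = 21.4, so it is affected only below 21.4.
- 40%: 15/0.60 = 25.0, so it is affected only below 25.
- 57%: beyond the limit at every baseline, because the stop never needs more than a 50% fall.

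If baselines were uniform on 20 to <30 (an assumption), the affected shares of that range are (21.4 − 20)/10 = 14% for the 30% row, (25 − 20)/10 = 50% for the 40% row, and 100% for the 57% row.

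**Step 3: what is still counted.** The triggering sample and its 48-hour repeat are both taken before the stop, and the repeat also goes to the central laboratory. A patient at 57% or more on both central values is counted. At b = 22, a confirmed 14.9 is a fall of 1 − 14.9/22 = 32.3% and enters the 30% row. At b = 20, 14.9 is a fall of 25.5% and enters only the 25% row. If that patient's eGFR falls further and this is seen only from day 6 onward, the deeper rows miss it.

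**Step 4: size, under assumptions.** Simulation of the 57% row. Assumed: a true fall heading to 65%, linear over 14, 28 or 42 days; onset uniform on Days 1 to 60; 7% measurement CV; scheduled visits; a 48-hour repeat at the stop limits; weekly repeats at falls of 30% or more; four weekly samples after stopping. Shares of such patients counted at baseline 25, for the three speeds:

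| After stopping | Both samples on treatment | First sample on treatment | All post-baseline samples |
|---|---|---|---|
| Keeps falling | 75, 50, 19% | 88, 65, 35% | 100, 100, 97% |
| Recovers (14-day time constant) | 74, 50, 18% | between its neighbours, so the same | 74, 50, 18% |

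With continued fall the loss is 25, 50 and 78 points if both samples must be on treatment, and 12, 35 and 62 points if only the first must be. With recovery it is zero. At baseline 40 recovery also gives equal counts (89, 75, 41% both ways). If eGFR plateaus on stopping, the loss is about 3 to 10 points (first sample only) or 14 to 29 points (both samples). The ends of these ranges move by a few points with small changes in the assumed sampling.

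**Step 5: the confirming sample.** The SAP does not say whether the confirming central value must also fall within the 5 days. Its 14-day confirmation rule follows the discontinuation-criteria row, and it is unclear whether it also governs the threshold rows. Step 4 shows that the answer changes the count. It also matters for a fall first seen at the end-of-treatment visit (Day 85), because the next scheduled central sample is at Day 113.

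**The case against.** An on-treatment summary is a legitimate choice when the aim is to attribute falls to drug. Patients with a centrally confirmed crossing are not hidden: they enter the discontinuation-criteria row, which has an added analysis without a time limit on confirmation. Other outputs reach later, namely by-visit central eGFR with no stated on-treatment limit, renal preferred terms to 28 days after last dose, the residual-fall row, and full laboratory listings. The only patient data on AZD9977 in the protocol (Table 2, phase 1b study) describe small eGFR decreases that improved after last dose, which points to the recovery case and no loss. All of this stands, and it limits the point to the depth recorded for late deepening or late confirmation. It does not fill that gap: the residual-fall row is one threshold at one visit, and the by-visit summary has no row for unscheduled weekly samples.

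The eGFR <30 group is also conditional. Protocol 5.1 currently requires eGFR of at least 30, with 20 to <30 opened only by decision of the safety committee, so the 20% share is a target.

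A reader might infer three stronger things that the documents do not support:

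- That the stop rule cuts off the 57% row. Step 3 shows that it does not.
- That the 30% and 40% rows fail across the whole eGFR <30 group. They are affected only below 21.4 and 25.
- That the combined discontinuation row is a defect because it means a smaller relative fall at low baselines. The row mirrors the protocol rule, randomisation is stratified by eGFR, and all arms within a category face the same rule.

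The limits in Step 1 apply to central values. A local trigger can stop drug at a somewhat different central fall, so they are not exact ceilings.

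**Conclusion.** The mismatch is real but narrow. The threshold rows leave out central values that Appendix F 2 requires after a renal stop. This can understate falls of at least 57% at any baseline, at least 40% below baseline 25, and at least 30% below baseline 21.4. The documents do not give the size. It runs from nil with recovery, through modest or moderate with a plateau, to large only if eGFR keeps falling off drug, and all of these rest on the assumed trajectories in Step 4. A general claim that the most severe renal declines are undercounted is therefore not established. The change is still worth making, because the values are already to be collected and the SAP already shows two windows for hypotension and renal adverse events.

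**What to change.** In SAP 4.11.3, keep the on-treatment rows. Beside them add the same four thresholds on all post-baseline central values through the safety follow-up visit, including the repeat and weekly samples from Appendix F 2. State whether the confirming sample may fall outside the 5-day window, and whether the 14-day rule applies to these rows. Optionally, show the two components of the renal discontinuation row (decline above 50%; value below 15) separately within each eGFR category, as a display aid.

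The cost is a few sentences of SAP text and some added table rows from data already required. The downside is that the added rows mix in off-treatment values, which is why both versions should appear. No change to the stopping rule is proposed.

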Appendix G COVID-19 Specifics

G 1 Background to COVID-19

There is currently an outbreak of respiratory disease (COVID-19) caused by a novel SARS-CoV-2 that was first detected in Wuhan City, Hubei Province, China in 2019. This new virus has rapidly spread across the globe causing the WHO to declare a pandemic situation on 12 March 2020. The countermeasures initiated by national and local governments worldwide and the recommendations issued by the health authorities have impacted current and new clinical studies. As the threat of pandemic burden including new outbreaks, locally or globally, will impact the further conduct of clinical studies, appropriate risk assessments and mitigation measures will need to be taken into consideration in all clinical studies to protect subjects, site staff, and society as a whole.

Both EMA and FDA as well as national health authorities in Europe have issued new guidelines that aim to provide recommendations for actions for conduct of clinical studies of medical products during COVID-19 pandemic. Since the pandemic situation is evolving, guidelines, recommendations, national laws, and local restrictions may change at high pace. Given the circumstances of potentially relapsing pandemic or epidemic situation with regard to the spread of COVID-19 in future, special attention will be paid to protect subjects participating in the study and site staff involved in the investigations against infection with SARS-CoV-2 as requested by the newly issued EMA guideline.

G 2 Risk Assessment for COVID-19 Pandemic

Risk of infection with SARS-CoV-2

The 2 study drugs with different mechanisms of action are unlikely to impact on the course of infection with SARS-CoV-2. Dapagliflozin is an anti-glycaemic agent and AZD9977 is a selective mineralocorticoid receptor modulator; neither is expected to cause immune suppression. Therefore, risk of the participants exposure to SARS-CoV-2 or to suffer from COVID-19 is expected to be similar to the background population with the same co-morbidities, in particular HF and CKD. The risk of exposure to infected people cannot be completely excluded as the participants may need to be in public areas (eg, commute to the site) and have additional human contact (eg, with site staff and other participants of the clinical study).

Measures to mitigate the additional risks caused by COVID-19 are:

• This study is going to start enrolling only when the Sponsor and CRO in collaboration deem it is safe to start the study. In addition, the study will not start until the local confinement measures or other safety restrictions linked to the COVID-19 pandemic imposed by the local authorities are compatible with safe conduct of the study.

- Current national laws and local recommendations for prevention of pandemic will be strictly adhered to.
- Participants will be closely monitored for any signs and symptoms of COVID-19, including fever, dry cough, dyspnoea, sore throat, and fatigue throughout the study during the pandemic. Once clinical signs of infection are reported by participants, the Investigator needs to determine whether samples can be collected, and safety data can be recorded on site. If not, AEs and concomitant medications will be obtained via phone calls. The decision to continue with dosing the participant with the study drugs in the event of him/her showing symptoms of COVID-19 infection will be per Investigator's discretion.
- The probability of virus transmission will be controlled as much as possible by:
 - Advice for participant to adhere to local requirements for reduction of the public exposure while ambulatory.
 - Confirmation of COVID-19 infection by optional laboratory assessment will be conducted based on availability (test capacity and turnaround time) of approved tests and on Investigator's discretion.
 - Requesting all participants are contacted by phone 1 day prior to every visit for assessing COVID-19 symptoms and signs and are asked not to attend the site in case of suspected reports. In addition, participants are asked for any contact with a person who has tested positive for SARS-CoV-2. If applicable, participants will be referred to the local health care system for further follow-up and treatment.
 - Physical distancing and person-to-person contact restrictions will be applied during site visits.
 - Where physical distancing is not possible, personal protective equipment will be used by study participants (surgical face mask, gloves) and staff (for example but not limited to masks, gloves, protectors, medical suits) if deemed appropriate by the Investigators and site staff and guided by local requirements.
 - Logistical improvements of the site and structural measures of the study site building will be implemented to further improve physical distancing.
- If site visits are not possible due to local restrictions, home nursing visits may be considered after discussion with and approval by the Sponsor.

Risk Related to COVID-19 vaccination

The 2 study drugs are predicted to have a low risk of influencing COVID-19 vaccine effectiveness and no additional safety concerns are anticipated. Clinical trial participant who have already taken the COVID-19 vaccine of any type are permitted to enrol in the study. Clinical trial participant who are not yet vaccinated should consider current/local guidelines, vaccine availability, and benefit-risk assessment of the COVID-19 vaccine. Ultimately, the

decision to vaccinate will be based on the judgment of the treating physician taking into account the participant's best interest.

G 3 Restrictions Related to COVID-19

During the COVID-19 pandemic, participants are advised to adhere to local requirements for reduction of the public SARS-CoV-2 exposure while ambulatory. If applicable, prior to screening (Visit 1a), potential participants should be called to confirm they are not experiencing any COVID-19 symptoms and signs and are asked not to attend the site in case of suspected infection. If appropriate, participants will be referred to the local health care system. Physical distancing and person-to-person contact restrictions will be applied and explained to participants while staying at the study site. Where physical distancing is not possible, study participants will be asked to use surgical face masks and/or gloves if deemed appropriate by the Investigator and site staff and guided by local requirements.

G 4 Data Quality Assurance Related to COVID-19

Monitoring visits at site will be limited to a minimum required as deemed appropriate during COVID-19 pandemic, per local regulations.

In addition, where possible, other measures for carrying out protocol related activities, such as but not limited to home nursing, may be employed as required.

G 5 References

Guidance on the Management of Clinical Trials during the COVID19 (Coronavirus) pandemic, EMA, Version 3 (28/04/2020). https://ec.europa.eu/health/sites/health/files/files/eudralex/vol-10/guidanceclinicaltrials_covid19_en.pdf

Appendix H Strong and Moderate Cytochrome P450 3A4 (CYP3A4) Inhibitors and Inducers

Strong or moderate CYP3A4 inhibitors or inducers are prohibited at least 3 weeks prior to randomisation (ie, start of run-in period) and for the duration of the study.

The following list (Table 8) is not intended to be exhaustive and a similar restriction will apply to other agents that are known to modulate CYP3A4 activity. Appropriate medical judgement is required. Please contact AstraZeneca with any queries you have on this issue.

Table 8 CYP3A4-Interacting Medication that are Prohibited During the Study

Medication	Rationale
Boceprevir, cobicistat, danoprevir and ritonavir, elvitegravir and ritonavir, grapefruit juice, indinavir and ritonavir, itraconazole, ketoconazole, lopinavir and ritonavir, paritaprevir and ritonavir and (ombitasvir and/or dasabuvir), posaconazole, ritonavir, saquinavir and ritonavir, telaprevir, tipranavir and ritonavir, telithromycin, troleandomycin, voriconazole	Strong CYP3A4 inhibitors which may increase AZD9977 concentrations.
Apalutamide, carbamazepine, enzalutamide, mitotane, phenytoin, rifampin, St. John's wort	Strong CYP3A4 inducers which may decrease AZD9977 concentrations.
Aprepitant, ciprofloxacin, conivaptan, crizotinib, cyclosporine, diltiazem, dronedarone, erythromycin, fluconazole, fluvoxamine, imatinib, tofisopam, verapamil	Moderate CYP3A4 inhibitors which may increase AZD9977 concentrations.
Bosentan, efavirenz, etravirine, phenobarbital, primidone	Moderate CYP3A4 inducers which may decrease AZD9977 concentrations.

H1 Reference

FDA guidance – Drug Development and Drug Interactions: Table of Substrates, Inhibitors and Inducers (content current as of 10 March 2020). Available at https://www.fda.gov/drugs/drug-interactions-labeling/drug-development-and-drug-interactions-table-substrates-inhibitors-and-inducers. Accessed on 9 June 2020.

